### **Secondary Endpoints:**

- The percentage of subjects with clinical remission at week 8 and 56 (in week 8 responders)

; The frequency and proportion of subjects with clinical remission at week 8 and 56 will be presented.

- The percentage of subjects with steroid-free remission at week 8 and 56 (in week 8 responders)

; The frequency and proportion of subjects with steroid-free remission at week 8 and 56 will be presented.

- The percentage of subjects with mucosal healing at week 8 and 56 (in week 8 responders)

; The frequency and proportion of subjects with mucosal healing at week 8 and 56 will be presented.

- The change of partial Mayo score from baseline overtime

; The descriptive statistics (the number of patients, mean, standard deviation, min, max) for partial Mayo score according to study visit and the change from baseline overtime will be presented.

- The change of the composition of Fecal micro biota from baseline at week 56
- The mean change of Fecal calprotectin level from baseline at week 56

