2.5.1 ITT Set

The ITT set will include all subjects intended to treat with adalimumab.

At week 8, all subjects who have received adalimumab treatment at least once will be included and, at week 56, all subjects who have clinical response at week 8 will be included.

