For the partial Mayo score, descriptive statistics (number of patients, mean, standard deviation, median, 1st quartile, 3rd quartile, minimum, maximum) will be presented at each visit by dividing the subjects into two groups according to the clinical response at visit 8 (week 56). T-test or Wilcoxon rank sum test will be performed to determine if there is a difference in the mean partial Mayo score depending on the clinical response.

In addition, for the difference in the change of the partial Mayo score at each visit from visit 1 (baseline), the descriptive statistics (number of patients, mean, standard deviation, median, 1st quartile, 3rd quartile, minimum, maximum) will be presented for each group. Paired t-test or Wilcoxon signed rank test will be performed to determine if there is a difference in the change within the group at each visit compared to visit 1 (baseline).

(6) Changes in the full Mayo score at visit 2 (week 8) and visit 8 (week 56) from visit 1 (baseline)

For the full Mayo score, the descriptive statistics (number of patients, mean, standard deviation, median, 1st quartile, 3rd quartile, minimum, maximum) will be presented at visit 1 (baseline), visit 2 (week 8), and visit 8 (week 56) by dividing the subjects into two groups according to the clinical response at visit 8 (week 56). T-test or Wilcoxon rank sum test will be performed to determine if there is a difference in the mean full Mayo score depending on the clinical response.

In addition, for the difference in the change of the full Mayo score at visit 2 (week 8) and visit 8 (week 56) from visit 1 (baseline), the descriptive statistics (number of patients, mean, standard deviation, median, 1st quartile, 3rd quartile, minimum, maximum) will be presented for each group. Paired t-test or

Wilcoxon signed rank test will be performed to determine if there is a difference in the change within the group at each visit compared to visit 1 (baseline).

(7) Changes in the rectal bleeding subscore at visit 2 (week 8) and visit 8 (week 56) from visit 1 (baseline)

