For the rectal bleeding subscore, the descriptive statistics (number of patients, mean, standard deviation, median, 1st quartile, 3rd quartile, minimum, maximum) will be presented at visit 1 (baseline), visit 2 (week 8), and visit 8 (week 56) by dividing the subjects into two groups according to the clinical response at visit 2 (week 8) and visit 8 (week 56). T-test or Wilcoxon rank sum test will be performed to determine if there is a difference in the mean rectal bleeding subscore depending on the clinical response.

In addition, for the difference in the change of the rectal bleeding subscore at visit 2 (week 8) and visit 8 (week 56) from visit 1 (baseline), the descriptive statistics (number of patients, mean, standard deviation, median, 1st quartile, 3rd quartile, minimum, maximum) will be presented for each group. Paired t-test or Wilcoxon signed rank test will be performed to determine if there is a difference in the change within the group at each visit compared to visit 1 (baseline).

(8) Mean change in the fecal calprotectin level^a at visit 2 (week 8) and visit 8 (week 56) from visit 1 (baseline)

For the fecal calprotectin level^a, the descriptive statistics (number of patients, mean, standard deviation, median, 1st quartile, 3rd quartile, minimum, maximum) will be presented at each visit for the following subgroups. T-test or Wilcoxon rank sum test will be performed to determine if there is a difference between the groups within each subgroup.

- Depending on the clinical response at visit 2 (week 8)
- Depending on the clinical response at visit 8 (week 56)
- Depending on the clinical remission at visit 2 (week 8)
- Depending on the clinical remission at visit 8 (week 56)
- Depending on the mucosal healing at visit 2 (week 8)
- Depending on the mucosal healing at visit 8 (week 56)

^a Fecal calprotectin level: The below the quantification limit (BQL) value of the fecal calprotectin level is <39.000 mg/kg, and when collected like this, it will be analyzed by replacing it with 39.000 mg/kg, and the total number of replacements will be specified.

| | | Last Update Date |
|----------------------------------|---|------------------|
| dreamcis ATIGERMED COMPANY | CONFIDENTIAL: THIS DOCUMENT AND THE INFORMATION CONTAINED HEREIN ARE PROPRIETARY TO THE COMPANY AND ARE NOT TO BE DISCLOSED. | 02-NOV-2018 |
| | WITHOUT THE WRITTEN PERMISSION OF THE COMPANY. | 02 1.0 . 2010 |
| STATISTICAL ANALYSIS PLAN (V2.0) | | |

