(9) Mean change in the hemoglobin level at visit 2 (week 8) and visit 8 (week 56) from visit 1 (baseline)

For the hemoglobin level, the descriptive statistics (number of patients, mean, standard deviation, median, 1st quartile, 3rd quartile, minimum, maximum) will be presented at each visit for the following subgroups. T-test or Wilcoxon rank sum test will be performed to determine if there is a difference between the groups within each subgroup.

- Depending on the clinical response at visit 2 (week 8)
- Depending on the clinical response at visit 8 (week 56)
- Depending on the clinical remission at visit 2 (week 8)
- Depending on the clinical remission at visit 8 (week 56)
- Depending on the mucosal healing at visit 2 (week 8)
- Depending on the mucosal healing at visit 8 (week 56)
- (10) Mean change in the albumin level at visit 2 (week 8) and visit 8 (week 56) from visit 1 (baseline)

For the albumin level, the descriptive statistics (number of patients, mean, standard deviation, median, 1st quartile, 3rd quartile, minimum, maximum) will be presented at each visit for the following subgroups. T-test or Wilcoxon rank sum test will be performed to determine if there is a difference between the groups within each subgroup.

- Depending on the clinical response at visit 2 (week 8)
- Depending on the clinical response at visit 8 (week 56)
- Depending on the clinical remission at visit 2 (week 8)
- Depending on the clinical remission at visit 8 (week 56)
- Depending on the mucosal healing at visit 2 (week 8)
- Depending on the mucosal healing at visit 8 (week 56)
- (11) Mean change in the CRP level at visit 2 (week 8) and visit 8 (week 56) from visit 1 (baseline)

For the CRP level, the descriptive statistics (number of patients, mean, standard deviation, median, 1st quartile, 3rd quartile, minimum, maximum) will be presented at each visit for the following subgroups. T-test or Wilcoxon rank sum test will be performed to determine if there is a difference between the groups within each subgroup.

- Depending on the clinical response at visit 2 (week 8)
- Depending on the clinical response at visit 8 (week 56)

| dreamcis ATIGERMED COMPANY | | Last Update Date |
|------------------------------------|---|------------------|
| | CONFIDENTIAL: | |
| | THIS DOCUMENT AND THE INFORMATION CONTAINED HEREIN ARE PROPRIETARY TO THE COMPANY AND ARE NOT TO BE DISCLOSED | 02-NOV-2018 |
| | WITHOUT THE WRITTEN PERMISSION OF THE COMPANY. | |

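### SAP 6.3.2 gives no all-patient change from baseline for partial Mayo or fecal calprotectin, and in (5)–(7) tests scores at the visits that define the response groups

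*SAP*

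**What the plan says.** **Endpoints.** Protocol 9.1 and 9.7 name change in partial Mayo over time and mean change in fecal calprotectin at week 56 as secondary endpoints, with no responder split. For partial Mayo, protocol 9.7 plans ungrouped descriptive statistics "for partial Mayo score according to study visit and the change from baseline overtime will be presented". SAP 4.1.2 (5) and (7) list both changes again and add hemoglobin, albumin, CRP and ESR.

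**Methods for the Mayo scores.** SAP 6.3.2 (5) summarises partial Mayo at each visit "by dividing the subjects into two groups according to the clinical response at visit 8 (week 56". A t-test or rank-sum test is to "determine if there is a difference in the mean partial Mayo score depending on the clinical response". Change from baseline is then given for each group, with a paired test to "determine if there is a difference in the change within the group at each visit compared to visit 1 (baseline". Item (6) does the same for full Mayo. Item (7) does so for rectal bleeding, "by dividing the subjects into two groups according to the clinical response at visit 2 (week 8) and visit 8 (week 56".

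**Methods for the laboratory values.** In item (8) the calprotectin statistics "will be presented at each visit for the following subgroups", followed by six splits: response, remission and mucosal healing, each at week 8 and week 56. Items (9)–(12) use the same template. The heading of (9), for example, reads "Mean change in the hemoglobin level at visit 2 (week 8) and visit 8 (week 56) from visit 1 (baseline", but the text below it describes levels only.

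**Analysis set.** Under SAP 2.5.1, "at week 56, all subjects who have clinical response at week 8 will be included".

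**The concern.** A single-arm effectiveness study should be able to state how much patients improved on average. A report that follows 6.3.2 would give partial Mayo change only by later outcome, and no calprotectin change statistic at all. Grouping by a week-56 outcome also means that a week-8 result is shown only for patients selected on what happened later.

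The second difficulty is overlap. Response is a fall in full Mayo plus a rectal bleeding condition, and partial Mayo is three of the four full Mayo items. Testing these scores between responders and non-responders, at the visit used to classify them, mostly re-tests the classification. Small p-values there could be read as findings.

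**Working it through.** **1. Is an all-patient change specified elsewhere in the SAP?**

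| Place | Content | All-patient change? |
|---|---|---|
| 4.1.2 | names the endpoints | no method |
| 6 | general list of summary statistics | no population, no change |
| 6.2 | baseline calprotectin | baseline only |
| 6.3.2 (5) | partial Mayo values and change | within week-56 groups only |
| 6.3.2 (8) | calprotectin levels by subgroup | no change statistic |
| 6.5 (2) | percentage below 250 by visit | not a change |

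The figure under item (5) is not available, so nothing is inferred from it.

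**2. Who is left out of item (5)?** The plan's size reproduces. With p = 0.75 and a total 95% CI width of 0.15, the exact (Clopper–Pearson) interval first meets the width at n = 139, and 139 / 0.95 = 146.3, rounded up to 147. On those figures:

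- week-8 responders: 139 × 0.75 = 104
- week-8 non-responders: 139 − 104 = 35, and 35 / 139 = 25%

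The 35 are non-responders only. SAP 6.3.2 excludes patients with an uncollected Mayo item and 6.6 does not replace endoscopy, so responders without a week-56 full Mayo score would also drop out. If 10% to 30% of responders lacked one (my assumption), 94 to 73 would remain, and 45 to 66 of 139 (32% to 47%) would be absent.

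**3. What does the selection do to the week-8 mean?** With assumed scores giving 77–80% week-8 response, close to the plan's 75%, mean partial Mayo change is −2.7 to −3.1 in all patients and −3.1 to −3.7 in week-8 responders. The range reflects within-patient correlation from 0.7 to 0.

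**4. How far does the definition fix the result?** I enumerated all subscores with baseline endoscopy 2–3, baseline total at least 6 and follow-up items 0–3. Response is a fall of at least 3 points and at least 30%, with rectal bleeding down by at least 1 or at most 1.

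- Qualifying combinations: 7,585.
- Partial Mayo rises in 0 and is unchanged in 288 (288 / 7,585 = 3.8%). The reason is simple: endoscopy can fall by at most 3, so a total fall of 3 leaves no room for a rise in the other items.
- Rectal bleeding is unchanged in 1,042 (13.7%) and worse in 310 (4.1%), so its paired test is not predetermined.

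**5. How often would the tests reject?** The simulation used one common score distribution, week-8 responders only, n = 73 or 94, item-level within-patient correlation 0 to 0.7 and 400 runs per setting; all of this is assumed.

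| Test | Rejection rate at 0.05 |
|---|---|
| Week 56 between groups, partial Mayo | 92–100% |
| Week 56 between groups, full Mayo | 98–100% |
| Week 56 between groups, rectal bleeding | 92–100% |
| Baseline partial Mayo between groups | 47–81% at correlation 0; 8–13% at 0.7 |
| Weeks 24 and 48 partial Mayo between groups | 2–7% at correlation 0; 13–23% at 0.7 |
| Unrelated laboratory value | 3–7% |

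A repeat at n = 73 and correlation 0.7 gave 88% for rectal bleeding, so roughly 90–100% is the fair summary for week 56. One of the three score settings gives only 18–30% week-8 response against the plan's 75%, and it contributes to these ranges. A second simulation with different item probabilities and independent visits gave 100% at week 56 and 5.2% at week 24 (full Mayo).

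Paired tests (n = 73) of full and partial Mayo were significant in 100% of runs for responders at week 56. They were also significant in 100% at week 8 among week-56 non-responders, because everyone retained had already responded at week 8.

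**The case against.** Protocol 9.7 still commits to ungrouped partial Mayo change, so for that endpoint the gap is a missing SAP row and not an abandoned endpoint. That stands.

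Pooling recovers part of what is missing. The two groups in (5) can be combined. The subgroup sizes and means in (8) give a mean calprotectin change if the same patients contribute at both visits, and the week-8 response split can cover all patients measured at week 8. Pooling does not give an SD or confidence interval for calprotectin change, and for (5) it cannot restore patients who are in neither group.

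Whole-cohort week-56 change is not available by design. Follow-up continues in week-8 responders, and protocol 9.2.2 ends data collection at discontinuation. This also stands, so later rows can describe only patients still followed.

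Two steps are inferences. Section 6.3.2 refers to the subjects without saying whether the 2.5.1 week-56 set applies, and the between-group test sentences in (5)–(7) name no visit; I take the visits from the descriptive sentence before them. The missing all-patient row does not depend on either.

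A reader might infer that every test in (5)–(12) is circular. The documents do not support that: intermediate visits, laboratory values and the rectal bleeding paired tests are not fixed by the response rule. No decision rests on these p-values in a single-arm descriptive study, which limits the harm.

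**Conclusion.** The point holds for secondary endpoints. SAP 6.3.2 (5) and (8) specify no all-patient change for two protocol secondary endpoints, and (8) specifies no change statistic even within groups. The same omission in (9)–(12) concerns markers that the SAP added, so it matters less.

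If the split follows SAP 2.5.1, about 35 of 139 patients (25%) are missing from item (5) on plan figures, plus responders without a week-56 full Mayo score. Under a wider reading of the split fewer are lost, but the all-patient row is still absent.

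The p-values that largely restate the definition are:

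- the between-group tests of partial Mayo, full Mayo and rectal bleeding at the post-baseline visit that forms the groups;
- the paired full and partial Mayo tests within responders at week 56;
- the week-8 paired tests in (5)–(6), if the split holds only week-8 responders.

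The direction follows from the definition; the exact rejection rates depend on assumed scores. The split tables and tests do not alter the primary endpoint or the sample size.

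It would be wrong to conclude from this that nothing here touches the primary endpoint. For a missing partial Mayo item, both 6.3.1 and 6.3.2 exclude the subject, while 6.6 carries the last value forward for clinical response. That separate conflict does reach the primary endpoint.

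**What to change.** - In 6.3.2 (5) and (8), add all-patient rows (n, mean and median change from baseline, 95% CI) for partial Mayo at each visit and calprotectin at weeks 8 and 56. Include week-8 non-responders at week 8, and state that later values describe patients still followed.
- In (9)–(12), add a change-from-baseline statistic to match the headings.
- In (5)–(7), drop the between-group p-values at the post-baseline visits that define the groups.
- In (5)–(6), drop the paired p-values within responders at week 56 and, if the split is limited to week-8 responders, the week-8 paired p-values in both groups.
- Keep the split tables as descriptive, and state who is in the split.
- As a separate edit, reconcile 6.3.1, 6.3.2 and 6.6 on missing partial Mayo items. Correcting 6.3.2 alone would leave the primary endpoint in conflict.

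The cost is SAP wording and table shells, with no new data, visits or patients. The downside is that some planned p-values are lost.

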6.4 Safety Endpoint Analysis Method

6.4.1 Adverse Events (AEs)

The AE status for each of the following items is presented in a summary table. In the summary table, the number of subjects with AE, incidence rate (%), 95% confidence interval for the incidence rate, and number of events will be included.

- AEs that caused discontinuation of the study drug
- Adverse drug reactions (ADRs)^a that caused discontinuation of the study drug
- Serious adverse events (SAEs) that caused discontinuation of the study drug
- Serious adverse drug reactions (SADRs)^a that caused discontinuation of the study drug
- SAEs that occurred during the entire study period

| dreamcis ATIGERMED COMPANY | | Last Update Date |
|----------------------------------|--|---------------------------------------|
| | CONFIDENTIAL: | · · · · · · · · · · · · · · · · · · · |
| | THIS DOCUMENT AND THE INFORMATION CONTAINED HEREIN ARE | 02-NOV-2018 |
| A LIGERMED COMPANY | PROPRIETARY TO THE COMPANY AND ARE NOT TO BE DISCLOSED WITHOUT THE WRITTEN PERMISSION OF THE COMPANY | 02-1NO V-2018 |
| | WITHOUT THE WRITTEN PERMISSION OF THE COMPANY. | |
| STATISTICAL ANALYSIS PLAN (V2.0) | | |

For the following items, the AE status will be presented in detail. Using MedDRA, the number of subjects, incidence rate (%), 95% confidence interval for the incidence rate, and number of events will be included by SOC and PT. Here, even if two or more events occurred in one subject, if they fall under one category, they will be analyzed as one subject in the category. Also, one subject may be presented as a duplicate in different AE categories.

- AEs that caused discontinuation of the study drug
- ADRs^a that caused discontinuation of the study drug
- SAEs that caused discontinuation of the study drug
- SADRs^a that caused discontinuation of the study drug
- SAEs that occurred during the entire study period

For the AEs that caused discontinuation of the study drug, the number of events for the AE items below will be presented.

- Severity
- Outcome
- Causality

As for "severity" and "causality" among the AE items, the AE status will be presented in detail. Using MedDRA, the number of subjects, incidence rate (%), and number of events will be included by SOC and PT. Here, even if two or more events occurred in one subject, if they fall under one category, they will be analyzed as one subject in the category. Also, one subject may be presented as a duplicate in different AE categories.

Based on the elapsed time since the first administration of the study drug, the AE incidence rate per 100 PTYs^c will be presented for the items below.

- AEs that caused discontinuation of the study drug
- SAEs that caused discontinuation of the study drug

For the items below, the list for each subject will be presented.

- AEs that caused discontinuation of the study drug
- ADRs^a that caused discontinuation of the study drug
- SAEs that caused discontinuation of the study drug
- SADRs^a that caused discontinuation of the study drug
- SAEs that occurred during the entire study period

| dreamcis ATIGERMED COMPANY | | Last Update Date |
|----------------------------------|---|------------------|
| | CONFIDENTIAL: | |
| | THIS DOCUMENT AND THE INFORMATION CONTAINED HEREIN ARE PROPRIETARY TO THE COMPANY AND ARE NOT TO BE DISCLOSED | 02-NOV-2018 |
| | WITHOUT THE WRITTEN PERMISSION OF THE COMPANY. | |
| STATISTICAL ANALYSIS PLAN (V2 0) | | |

STATISTICAL ANALYSIS FLAN (V2.U)

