### **9.2.2 Drop-Out Subjects**

Once a subject is dropped out from the study, no further information for that subject will be collected. However, the reason for drop-out will be reported and serious adverse events will be reported to AbbVie until 70 days following the intake of the last dose of adalimumab.

Subjects will be dropped out from the study:

- 1) If the subjects choose to withdraw from the study
- 2) Where ethical or practical conflicts hinder the procedure of the study, and such cases will be determined based on the investigator's judgment
- 3) In case of Adalimumab discontinuation at any point during study period

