### **9.7.1 Safety Analysis**

The serious adverse event · adverse drug reaction will be coded by MedDRA latest version.

The cumulative total number and percentage of subjects reporting serious adverse event · adverse drug reaction will be tabulated. Also, AEs leading to discontinuation of adalimumab will be collected and tabulated.

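### SAP 6.4.1 reports adverse drug reactions only when they caused discontinuation, so no planned summary table, on its natural reading, identifies other related SAEs as related

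*SAP*

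**What the plan says.** Protocol 9.7.1 plans to tabulate "The cumulative total number and percentage of subjects reporting serious adverse event", followed by a centred dot and the term adverse drug reaction. No limit to discontinuations is attached. The next sentence then adds a further item: "Also, AEs leading to discontinuation of adalimumab will be collected and tabulated".

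SAP 6.4.1 is built in two parts: events that caused discontinuation, and SAEs over the whole study. In the summary table the serious-reaction item is "Serious adverse drug reactions (SADRs)^a that caused discontinuation of the study drug"; in the listings it is "SADRs^a that caused discontinuation of the study drug". The severity, outcome and causality counts open with "For the AEs that caused discontinuation of the study drug, the number of events for the AE items below will be presented". The only item free of the restriction is "SAEs that occurred during the entire study period".

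On collection, Protocol 9.2.2 makes stopping adalimumab a reason for drop-out ("In case of Adalimumab discontinuation at any point during study period"), but states that after drop-out "serious adverse events will be reported to AbbVie until 70 days following the intake of the last dose of adalimumab". Protocol 11.1.5 has SAEs actively solicited and non-serious events not.

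On causality, Protocol 11.1.3 has two levels, Reasonable Possibility and No Reasonable Possibility. SAP footnote a (printed within 6.5) counts four labels as ADRs: probable, possible, probably not, and not assessable.

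**The concern.** An SAE judged related to adalimumab need not lead to stopping. Treatment may continue, or the event may begin after the last dose but inside the 70-day reporting window. An event of the second kind cannot have caused a discontinuation that had already happened. The protocol foresees both kinds and collects them, yet the SAP's related-event counts leave both out.

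A reader of the tables would see how many subjects had an SAE, but the serious-ADR row would cover only part of those judged related. Someone who did not notice the qualifier could take that row for the total of related serious events. The ADR figures that are reported also rest on causality labels that differ from the protocol's scale.

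**Working it through.** No figure in the plan bears on this point, so the check is an inventory of SAP 6.4.1 set against the protocol.

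1. Output items in SAP 6.4.1:

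| Output | Items | ADR or serious-ADR items | Of these, limited to discontinuation | Whole-study SAE items |
|---|---|---|---|---|
| Summary table | 5 | 2 | 2 | 1 |
| SOC/PT tables | 5 | 2 | 2 | 1 |
| Severity, outcome, causality counts | 1 | 0 | – | 0 |
| Severity and causality by SOC/PT | 1 | 0 | – | 0 |
| Rates per 100 PTYs | 2 | 0 | – | 0 |
| By-subject listings | 5 | 2 | 2 | 1 |
| Total | 19 | 6 | 6 | 3 |

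All 6 ADR or serious-ADR items carry the discontinuation limit. None of the 3 whole-study SAE items states a relatedness split. Both rates are limited to discontinuation events. So are the severity, outcome and causality counts, by their opening words. The paragraph on severity and causality by SOC/PT does not restate its population. It refers back to the items just listed for discontinuation AEs, so the restricted reading is the natural one, but it is not explicit.

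2. What Protocol 9.7.1 asks for depends on the dot:
   - Serious AEs and serious ADRs: the SAP lacks the whole-study serious-ADR count.
   - SAEs and ADRs: the SAP delivers the SAE count but lacks the ADR count.
   - One combined count of serious events and reactions: serious ADRs are a subset of SAEs, so the whole-study SAE row satisfies it.

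   The first two are the more natural readings. On both, the discontinuation events are an addition to the tabulation and do not define its scope.

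3. Following one event through the outputs: take an SAE judged related, with treatment continued or with onset in the 70-day window. It enters the three whole-study SAE items. It enters none of the six ADR items, neither rate and, on the natural reading, neither severity/causality output. Whether the listing would show it as related is unknown, because the SAP specifies no listing columns.

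4. Causality scale: the SAP has 4 labels that count as ADR, the protocol has 2 levels, and neither document gives a mapping. The SAP's ADR count therefore cannot be shown to equal the Reasonable Possibility count.

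5. Scale: one subject at the planned maximum enrolment is 1/147 = 0.0068, or 0.68 percentage points. Safety is analysed in the ITT set (SAP 2.5.3), so with fewer subjects each one weighs slightly more.

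**The case against.** The strongest defence is that the two-part structure follows the data. The protocol commits to collecting SAEs and AEs leading to discontinuation; non-serious events arrive only as spontaneous reports. A whole-study table of all ADRs would be incomplete, and the SAP's revision table shows that the structure was deliberate. This stands against a table of all ADRs. It does not explain the absence of whole-study serious ADRs, which come from SAEs that are actively solicited, and the revision table gives no reason for leaving them out.

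A second defence is that nothing is shown to be lost. Every SAE is counted, coded and listed, and with at most 147 subjects related ones could be counted from a listing that carries causality. This stands in part: silence about columns does not show that causality is missing. But a listing is not the number and percentage that 9.7.1 plans.

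Three stronger readings are tempting. A reader might infer that the SAP contradicts Protocol 9.7.1 however that section is read; the combined-count reading prevents that conclusion. A reader might infer that related SAEs disappear from the report; they do not, since they remain in the SAE totals and the listing. A reader might infer that the SAP's ADR definition hides reactions; counting the two weaker categories makes it inclusive, so any error is more likely over-counting, and its effect depends on the CRF, which is not available.

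**Conclusion.** The point holds as a minor gap. SAP 6.4.1 identifies ADRs and serious ADRs only among events that caused discontinuation, and gives whole-study SAEs no stated relatedness split. That falls short of Protocol 9.7.1 on its two most natural readings. A related SAE that did not cause discontinuation is not identified as related in any planned summary table.

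This rests on three assumptions: the severity and causality paragraph covers discontinuation AEs, as its context suggests; the whole-study SAE item includes the 70-day follow-up; and causality is recorded for all SAEs, as Protocol 11.1.3 implies. The number of affected events cannot be computed from the documents, and the 0.68 points per subject is a scale, not an estimate. No effectiveness endpoint, sample size or comparison is affected.

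**What to change.** In SAP 6.4.1:

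- Add serious ADRs over the whole study to the summary table and the SOC/PT tables, worded in parallel with the existing whole-study SAE item.
- State that the whole-study SAE listing shows causality and whether the event caused discontinuation. A separate serious-ADR listing is then unnecessary.
- State the population of the severity and causality paragraph.
- Show the probably not and not assessable categories on separate lines, and state how the CRF labels map to the two levels of Protocol 11.1.3, so that the Reasonable Possibility count can be recovered.
- Do not present a whole-study table of all ADRs as complete, because non-serious events are not actively solicited. Clarify in Protocol 9.7.1 or the SAP which tabulation the dot intends.

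The cost is SAP wording, one summary row, one SOC/PT table, two listing columns and a few extra causality lines. No new data are needed if causality is recorded for all SAEs; a written mapping is needed if the CRF uses the SAP's labels.
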